8.1.4 Other visits

8.1.4.1 *Early Termination visit*

Subjects who discontinue the study drug should remain in the study and will be asked to return for all remaining visits and assessments (including daily assessment of pruritus and sleep disturbance). Subjects who discontinue from the study will be fully assessed whenever possible: Subjects discontinued before the week 24 visit should attend an early termination visit (with procedures/assessments to be conducted outlined below) and a final visit (Section 8.1.3.2) 12 weeks after the last study drug administration; subject discontinued after the week 24 visit should attend a final visit (Section 8.1.3.2) 12 weeks after the last study drug administration.

During the early termination visit, the following procedures/assessments will be conducted:

1. Ask the subject to complete the DLQI, HADS and EQ5D questionnaires. Ask the subject about the missed work/school days since the last visit.
2. Collect information regarding AE (including review of laboratory values) and concomitant therapies/procedures.
3. Check subject's record for pruritus NRS, PCS and sleep disturbance NRS.
4. Complete the evaluation of EASI, IGA, and SCORAD (including BSA).
5. Perform a physical examination (including the evaluation of prurigo nodularis lesions if applicable), vital signs measurements and ECG.
6. Conduct respiratory medical assessments, including PEF for subjects with a history of asthma.
7. Complete UPT if the subject is a female of childbearing potential.
8. Collect urine for urinalysis.
9. Collect blood sample for hematology, blood biochemistry, PK and ADA.
10. Collect the returned TCS. Dispense TCS and, if needed, moisturizer, and provide instruction on their usage. Instruct subject to bring used and unused TCS back to investigational site at each visit.
11. Schedule the final visit (12 weeks after the last study drug administration).

8.1.4.2 *Unscheduled visit*

Subject should be reminded to adhere to the study schedule, and visits occurring outside of the visit window are not considered as unscheduled visit. Unscheduled visits may be necessary to repeat testing abnormal laboratory results or for follow-up of AEs. Assessments to be conducted at the unscheduled visit will depend on the reason for the visit: any of the listed procedures/assessments may be conducted but not all are required. However, blood sample collection for PK and ADA analyses are mandatory during unscheduled visits for safety reasons.

1. Collect information regarding AE (including review of laboratory values) and concomitant therapies/procedures.
2. Check subject's record for pruritus NRS, PCS and sleep disturbance NRS.
3. Complete the evaluation of EASI, IGA, and SCORAD (including BSA).
4. Perform a physical examination (including weight, and the evaluation of prurigo nodularis lesions if applicable), vital signs measurements and ECG.
5. Conduct respiratory medical assessments, including PEF for subjects with a history of asthma.
6. Complete UPT if the subject is a female of childbearing potential.
7. Collect urine for urinalysis.
8. Collect blood sample for hematology, blood biochemistry, TARC, PK and ADA. Blood sample for re-test of TB and/or CPK after the initial test may also be collected.
9. Collect the returned TCS. Dispense TCS and, if needed, moisturizer, and provide instruction on their usage. Instruct subject to bring used and unused TCS back to investigational site at each visit.

9 STATISTICAL METHODS PLANNED

9.1 Statistical and analytical plans

A Statistical Analysis Plan (SAP) will be developed as a separate document. The SAP will contain detailed and technical description of specific data conventions, calculations and of statistical procedures for executing the analyses that are specified in the sections of the clinical trial protocol below. Any changes made to analysis after finalization of SAP will be documented in the clinical study report.

The primary analysis will be performed after all randomized subjects have completed week 24 (excluding safety follow-up) visit or have withdrawn from the study. No one directly involved with the conduct of the study will see the unblinded data before the completion of the trial, in order to avoid biasing the remaining data of the study. The final analysis will be performed when the last subject has completed the study (i.e. completed the safety follow-up or has withdrawn from the study).

9.1.1 Data transformations

Details of any data transformation for endpoints will be provided in SAP.

9.1.2 Analysis populations

The following populations and evaluability criteria will be used to analyze the efficacy, safety, PK/PD and QoL endpoints. For the safety analyses, subjects will be analyzed as treated and for efficacy analyses subjects will be analyzed as randomized.

9.1.2.1 *Intent-to-Treat (ITT) population*

The ITT Population will consist of all randomized subjects. All efficacy endpoints will be analyzed based on the ITT population.

9.1.2.2 *Per-Protocol (PP) population*

The Per Protocol population will comprise all subjects in the ITT population who have no major protocol deviations that would have a significant effect on the efficacy of the study treatment. Only primary and selected secondary endpoints will be analyzed using PP population.

9.1.2.3 *Safety population*

The safety population will comprise all subjects in ITT population who receive at least one dose of study drug. Randomized subjects will only be excluded if there is a clear documented evidence that the subject did not receive any study drug injection. All safety data will be summarized based on the safety population.

9.1.2.4 *PK analysis population*

The PK analysis population will include all subjects in the safety population who provide at least one post-baseline evaluable drug concentration value.

9.1.3 Imputation of missing data

The primary method to impute the missing values will be as follows:

Continuous Endpoints: To impute the missing values for continuous endpoints, Mixed-effect Model for Repeated Measures (MMRM) approach will be used for the primary and secondary endpoints.

In addition, Multiple Imputation (MI), Last-Observation Carried Forward (LOCF), Worst-Observation Carried Forward, Observed Case (OC), and Pattern-Mixture Model under missing not at random assumption will be carried out as sensitivity analysis for primary and selected secondary endpoints.

Binary Endpoints: All missing values will be treated as a Non-Responder for the binary endpoints.

LOCF, OC, MI and Pattern-Mixture Model under missing not at random assumption approaches will be used as sensitivity analysis to impute the missing values for the selected secondary endpoints.

Use of rescue therapy: All efficacy data, except OC, will be set to missing after rescue medication is used. In OC analysis, no observed data after subject has received rescue treatment will be excluded.

There will be no imputations for missing laboratory, and vital sign data. Further details on imputation of missing data will be provided in the SAP.

9.1.4 Subgroup analysis

Descriptive summary and analysis for primary and selected secondary endpoints will be produced for the following subgroups:

- Region
- Age (18-65 or >65)
- Gender
- Race
- Baseline IGA (3 or 4)
- Baseline EASI (\leq median or $>$ median)
- Intrinsic or extrinsic AD (based on IgE and eosinophil counts)

9.1.5 Descriptive and inferential statistical analyses

9.1.5.1 Demography and baseline characteristics

Subject disposition, demographics, baseline characteristics, previous therapies, concomitant therapies and physical exams by treatment will be summarized by descriptive statistics. Pre and post-treatment therapies and procedures will be summarized separately.

9.1.5.2 Efficacy analyses

Primary inference for all the efficacy analyses will be based on the ITT population at the week 24 endpoint. PP analyses will be carried out as supportive analyses for the primary and selected secondary endpoints.

All efficacy variables will be summarized by treatment at each visit. The categorical variables will be summarized by frequency and percentage for each response category (N, %). The continuous variables will be summarized using means, medians, minimum, maximum, and standard deviations for the data collected at each visit.

9.1.5.2.1 Primary efficacy analysis

The primary endpoint is percentage change in EASI score from baseline to week 24.

The primary endpoint will be analyzed using a MMRM approach, including terms of treatment group, and baseline IGA severity. Visit will be fitted as a categorical variable, with the effect of treatment group and baseline IGA varying at each visit. An unstructured covariance will be used to model the within-patient errors in the analysis. A linear contrast will be used, within the MMRM framework, to estimate difference between nemolizumab dose levels and placebo. Other covariates may be explored and will be added into the model, if appropriate. Treatment difference for each nemolizumab dosing regimen versus placebo will be estimated along with associated 95% confidence intervals will be presented.

Multiple comparison procedures-modeling (MCP-Mod) approach will be applied using a set of candidate dose-response models to test for a dose-response relationship via model-associated statistics.

9.1.5.2.2 Secondary and other efficacy analysis

Continuous secondary efficacy endpoints will be analyzed similar to the analysis of the primary endpoint.

All categorical efficacy endpoints will be analyzed using Stratified Cochran Mantel-Haenszel test stratified by baseline IGA severity.

Time to use of rescue therapy and other time to event data will be summarized and analyzed using Kaplan-Meier method. Subjects who do not experience the event at any time will be censored at the last evaluation time.

Sponsor plans to perform further validation of the NRS responder analysis using anchor-based approach based on a Receiver Operating Curve analysis.

Further details on efficacy analyses will be provided in the SAP.

9.1.5.3 Safety analyses

All safety analyses will be based on the safety population. Summary of all safety endpoints will be presented for each treatment group.

9.1.5.3.1 Extent of exposure

The duration of exposure and the number of subjects exposed to study medication will be summarized by treatment group and visit. Number of subjects exposed will be presented by study periods (treatment period and follow-up period).

9.1.5.3.2 Adverse events

Treatment-emergent Adverse Events (TEAEs), defined as those AEs occurring after the first administration of study treatment until the last study visit, will be tabulated in frequency tables by System Organ Class and Preferred Term based on the Medical Dictionary for Regulatory Activities (MedDRA) for each study phase. Additional summary tables will be provided for SAEs, AEs related to the study drug and/or study procedure, AESIs, selected AEs, and AEs leading to treatment discontinuation and study withdrawal. For a given AE, a subject will be counted once even if he/she has experienced multiple episodes of that particular AE.

Pre-treatment AEs will be listed separately.

9.1.5.3.3 Clinical laboratory

Laboratory data (absolute values and change from baseline) will be summarized by visit and treatment group. In addition, the number and percent of subjects below, within, and above the laboratory reference ranges will be summarized by treatment group. Shift tables will be generated using the reference ranges.

Abnormal laboratory values from tests on baseline visit will not be considered as TEAEs, as the sample collection will be conducted prior to study drug administration.

9.1.5.3.4 Vital signs

All vital signs and weight data (absolute values and change from baseline) will be summarized by visit and treatment group. In addition, the number and percent of subjects with clinically significant abnormal values of clinical concern will be summarized by treatment group.

9.1.5.3.5 Peak Expiratory Flow (PEF)

PEF measurements (absolute values and change from baseline) will be summarized by visit and treatment group. Further details on safety analyses will be provided in the SAP.

9.1.5.4 PK parameters and ADA analyses

The PK parameters derived using non-compartmental techniques will be regarded as primary endpoints for the pharmacokinetic analyses (see details in Section 7.3.3). Primary inference for all the PK parameters will be based on the pharmacokinetic analysis population.

Descriptive statistics (n, arithmetic mean, standard deviation [SD], minimum, median, maximum) by treatment group will be calculated for all derived pharmacokinetic endpoints. Geometric means and between-subject coefficients of variation (CVb) will be calculated for log_e-transformed AUC_{0-28d}, C_{trough} and C_{max} where:

Following log_e-transformation, AUC_{0-28d}, C_{trough} and C_{max} will be analyzed separately using analysis of variance (ANOVA), fitting a model with treatment group as a fixed effect. The residual variance from the model will be used to calculate point estimates and 90% CIs for the least squares means for each treatment formulation on the log_e scale. These estimates will be back transformed to give point estimates and 90% CIs on the original scale.

The concentration at each time point will be summarized as arithmetic mean, standard deviation, median, minimum, and maximum, number of BLQs (Below the Limit of Quantification). PK parameters using geometric means will be compared to determine when steady state conditions are achieved during the treatment period.

The potential relationship between plasma concentrations of nemolizumab and change in EASI, pruritus NRS, biomarkers or other indicators of disease activity will be explored using PK/PD modeling, as appropriate.

Incidence of positive ADA results will be summarized by treatment group (absolute occurrence and percent of subjects). ADA results presentation will be detailed in the SAP.

9.1.5.5 Biomarker Analyses

Primary inference for all biomarker analyses (including eosinophil, TARC, IgE etc.) will be based on the observed cases. All biomarker variables (e.g. absolute and change from baseline) will be summarized and compared across treatments at each time point. If the variable is not Gaussian distributed then it will be log transformed. Student T-test will be used to compare the nemolizumab to placebo, where appropriate. P-values will be presented. In addition, a box-plot will be produced for each treatment group at each time point.

Missing values will not be imputed. False Discovery Rate approach ([Benjamini 1995](#)) or another appropriate approach will be used to control for multiplicity.

[figure not shown]

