Efficacy endpoints:	Primary efficacy endpoint 
 - Percent change from baseline in EASI to week 24 Secondary efficacy endpoints 
 - Proportion of subjects achieving IGA success (defined as IGA 0 [clear] or 1 [almost clear]) at each visit up to week 24 - Percent change from baseline in EASI at each visit up to week 24 - Absolute and percent change from baseline in weekly average of the peak and average NRS at each visit up to week 24 - Proportion of subjects with an improvement of weekly average pruritus peak NRS ≥ 4 from baseline to week 24 - Absolute and percent change in weekly average sleep disturbance NRS from baseline to week 24 - Proportion of subjects achieving PCS success (defined as a weekly prorated rounded average PCS ≤ 1 [none-mild]) at week 24 - Proportion of subjects achieving 50%, 75% or 90% reduction from baseline in EASI score (EASI-50, EASI-75, and EASI-90) at week 24 - Absolute and percent change in SCORing Atopic Dermatitis (SCORAD) score from baseline to week 24
Safety assessment:	
 - Adverse Events (AEs) including Adverse Event of Special Interest (AESI) and selected AEs at all visits - Physical examination and vital signs at all visits - Clinical laboratory values at screening, baseline, weeks 4, 8, 12, 16, 20, 24 & 32 - Electrocardiogram (ECG) at screening, baseline, weeks 1, 12 & 24 - Respiratory assessment at all visits in all subjects, and Peak Expiratory Flow (PEF) in subjects with a medical history of asthma 
An Independent Data Monitoring Committee (IDMC) will monitor the safety data at regular intervals throughout the clinical trial.

PK, pharmacodynamics (PD) and anti-drug antibody (ADA) assessment:	
 - Blood sample collection for PK at baseline, weeks 1, 2, 4, 8, 12, 16, 20, 24, 28, 32 and unscheduled visits for safety reasons - Blood sample collection for anti-drug antibody (ADA) assessment at baseline, weeks 4, 8, 16, 24, 32 and unscheduled visits for safety reasons - Blood sample collection for PD/ biomarker analyses at baseline, weeks 4, 8, 16, 24 & 32 - Blood sample collection for analysis of thymus and activation-regulated chemokine (TARC) at baseline, weeks 1, 2, 4, 8, 12, 16, 20, 24, 28 & 32 - Stratum corneum sample collection for skin biomarker analyses: baseline & week 16

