6.1.4 Randomization number

A randomization number will be allocated to each eligible subject at baseline by the IRT system. Randomization will be stratified by baseline IGA score (3 or 4).

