4.9.2 Biomarker Analyses

Primary inference for all biomarker analyses (including, but not limited to, eosinophil TARC, IgE, IL6, IL8, and IL18) will be based on the observed cases. All biomarker variables (using logarithm transformation) will be summarized across treatments at each time point.

Any observations in trends within the Biomarker data may be explored with PK/PD correlations/models. All of this analysis will be considered exploratory. The outputs will be in a separate report.

The detailed analysis will be carried out by Biomarker group in GALDERMA, and will be reported separately.

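### The only biomarker test named in either document is a t-test without covariates; ANCOVA on the baseline value and IGA stratum would be about as precise or more so, at almost no cost

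*Protocol*

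**What the plan says.** Protocol 9.1.5.5 sets the comparison out in two sentences: "All biomarker variables (e.g. absolute and change from baseline) will be summarized and compared across treatments at each time point", and "Student T-test will be used to compare the nemolizumab to placebo, where appropriate". Variables that are not Gaussian are log-transformed and p-values are presented. The analysis uses observed cases ("Missing values will not be imputed"), and a false-discovery-rate method "or another appropriate approach will be used to control for multiplicity". No covariate is mentioned.

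SAP 4.9.2 keeps observed cases as the basis for inference but says only: "All biomarker variables (using logarithm transformation) will be summarized across treatments at each time point". It names no test, p-value or model, and passes the detailed analysis to the sponsor's biomarker group for separate reporting. SAP 4.11, which lists changes from the protocol, does not mention biomarkers.

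The covariates are collected anyway. The protocol synopsis schedules "Blood sample collection for PD/ biomarker analyses at baseline, weeks 4, 8, 16, 24 & 32" and "Stratum corneum sample collection for skin biomarker analyses: baseline & week 16". TARC is also sampled at baseline, and Protocol 8.1.2.1 has hematology (which includes eosinophils) and IgE drawn at the baseline visit. Baseline IGA, 3 or 4, is the randomization stratum (Protocol 6.1.4).

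**The concern.** A two-sample t-test on absolute values ignores each subject's own starting level. A t-test on change uses it, but forces a slope of 1 on baseline, which is too steep when the two variances are equal and the correlation is below 1. ANCOVA estimates the slope, so it need not choose between them. Planning both t-tests also yields two p-values per marker, dose and visit, with no statement of which one counts.

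Most of the SAP's own modelling adjusts. The primary MMRM carries the baseline value and baseline IGA (SAP 4.7.2). The continuous sensitivity analyses (4.7.1.3), 5-D itch (4.7.4.9) and EQ5D (4.9.3.4) use ANCOVA with treatment, IGA and the baseline value. Neither document says why biomarkers should differ. At stake is precision in pharmacodynamic comparisons that also carry a multiplicity correction, where a real effect could be missed.

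**Working it through.** **Figures in the plan.** The biomarker sections give no effect size, SD, correlation or power. The only power statement (Protocol 9.2, SAP 4.10) is at least 90% for the MCP-Mod test on EASI. With the nine candidate shapes, 50 per arm, SD 45, a difference of 30 reached at 90 mg and one-sided 0.025, it recalculates to 0.928-0.983, so on that reading it reproduces. It supplies only n = 50 per arm here.

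**Assumptions.** Correlation rho between baseline and follow-up on the analysed scale, shown as a range; equal baseline and follow-up variance; all 50 per arm observed; one dose against placebo; two-sided 5% without multiplicity correction.

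**Formulas**, per-arm variance in units of the follow-up variance:
- t-test on absolute value: 1
- t-test on change: 2(1 - rho)
- ANCOVA: (1 - rho²) × [1 + 1/(2n - 4)], where the bracket is the price of estimating the slope; at n = 50 it is 1 + 1/96 = 1.0104

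Example, rho = 0.5: change = 2 × 0.5 = 1.00; ANCOVA = 0.75 × 1.0104 = 0.758. The ratio to either t-test is 0.758, a 24% reduction.

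| rho | Change | ANCOVA | ANCOVA / absolute | ANCOVA / change | Power at 0.5 SD: absolute / change / ANCOVA |
|---|---|---|---|---|---|
| 0 | 2.00 | 1.010 | 1.01 | 0.51 | 0.70 / 0.42 / 0.69 |
| 0.3 | 1.40 | 0.919 | 0.92 | 0.66 | 0.70 / 0.55 / 0.73 |
| 0.5 | 1.00 | 0.758 | 0.76 | 0.76 | 0.70 / 0.70 / 0.81 |
| 0.7 | 0.60 | 0.515 | 0.52 | 0.86 | 0.70 / 0.89 / 0.93 |
| 0.9 | 0.20 | 0.192 | 0.19 | 0.96 | 0.70 / >0.99 / >0.99 |

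The 0.5 SD effect is an illustration, not a figure from the documents.

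**From 80% power, rho = 0.5** (normal approximation). The t-test has standardized effect 1.96 + 0.84 = 2.80. Under ANCOVA it becomes 2.80 / √0.758 = 3.22, and 3.22 - 1.96 = 1.26 corresponds to about 90% power.

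**Simulation check.** Fitting treatment, baseline and a two-level stratum that had no effect on the outcome gave ANCOVA power of 0.70, 0.73, 0.81 and 0.93 at rho 0, 0.3, 0.5 and 0.7, in line with the table. This shows that the extra term costs little. It does not show that IGA adds precision.

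**If the variances differ.** Let the follow-up SD be k times the baseline SD. In units of the baseline variance, change has variance 1 + k² - 2·rho·k and ANCOVA has k²(1 - rho²), leaving out the 1% slope cost. At rho = 0.7:
- k = 1: 0.51 / 0.60 = 0.85
- k = 1.25: 0.797 / 0.8125 = 0.98
- k = 0.8: 0.326 / 0.52 = 0.63

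So rho alone does not fix the gain over change. The gain over absolute values, 1 - rho², does not depend on k.

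**The case against.** The strongest reply is that the SAP does not carry the t-test forward. It plans summaries and defers the detailed analysis to a report that is not among these documents, and the protocol's wording is permissive. A reader might infer that unadjusted t-tests will certainly be run. The documents do not support that: the biomarker group may already intend a covariate model. What stands is that the t-test is the only comparative test written down, that nothing replaces it, and that Protocol 9.1 promised the detailed procedures in the SAP.

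Other stronger readings also fail:
- *The plan ignores baseline.* It does not; the change comparison uses it, and at high correlation little is left to gain over that comparison.
- *Chance baseline imbalance passes in full into the absolute-value comparison.* Under the equal-variance model it enters multiplied by rho.
- *Adjustment is free and the gain is assured.* It costs 1-2 degrees of freedom and about 1% of variance at rho = 0, and the gain rests on a correlation that the documents do not give.
- *The SAP adjusts for IGA everywhere else.* The subgroup ANCOVA in SAP 4.7.2 includes the baseline value but lists no separate IGA term.
- *The biomarker p-values would be invalid.* Under randomization the t-test is a legitimate test; the issue is efficiency.

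It is also fair that the powers above are at an uncorrected 5% level with complete data. Under multiplicity control and with missing samples the absolute powers would be lower. The variance ratios do not depend on the significance level and change very little with modest loss of subjects.

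**Conclusion.** The point holds as an efficiency improvement of low severity. The stated biomarker test uses no covariates although suitable ones are collected, and the SAP neither replaces it nor records dropping it. Under equal variances, ANCOVA is within about 1% of the better t-test at worst (rho = 0) and clearly better than both at middling correlations. The gain vanishes against absolute values as rho nears 0 and against change as rho nears 1, and the gain over change shifts if the variances differ. No separate gain is shown for the IGA term; the case for it is that it is the stratification factor and costs one degree of freedom.

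A reader might go further and infer a threat to the trial's efficacy conclusions or its size. There is none: biomarkers are not among the primary, secondary or other efficacy endpoints, and the sample size rests on EASI.

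**What to change.** Before unblinding, state in SAP 4.9.2 or in the separate biomarker plan that each biomarker is compared at each time point by ANCOVA of the log value on treatment, log baseline of the same marker and IGA stratum (3 or 4), on observed cases, with each dose contrasted with placebo. Apply the false-discovery-rate correction to those p-values, in place of the two t-tests. With log baseline in the model, analysing the log value or the log change gives the same treatment estimate, so one p-value per marker, dose and visit is enough. List the departure from Protocol 9.1.5.5 in SAP 4.11.

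The cost is wording and a different model statement. No new data or visits are needed.
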